9.4.2 Pharmacodynamic Analyses

Pharmacodynamic endpoints with repeated post-baseline assessments will be analyzed using a mixed-model repeated measures (MMRM) analysis, including baseline score (if applicable), treatment, concomitant SSRI/SNRI use, visit, and the interaction between treatment group and visit as fixed factors in the model. Subject will be included as a random effect in the model.

The trial is designed as a learning trial instead of a confirmatory trial. The key research question for the pharmacodynamic endpoints will be primarily addressed with an estimand based on the following attributes: 1) treatments as randomized regardless of the final dose level achieved following the titration steps, 2) subjects in the modified intent-to-treat (mITT) population who tolerate dose increases to at least Step 4 on Day 21 during titration as the target trial population, 3) change from Baseline to Week 12 as the key endpoint of interest, 4) the treatment differences estimated based on the least square mean and the corresponding 80% confidence interval from the MMRM model as the population level summary, and 5) a hypothetical strategy to address intercurrent events (ICEs) of potential death, treatment discontinuations, missed visits, and start of prohibited concomitant medications unless a treatment-related reason can be identified for a given ICE. If such reasons are identified, a composite strategy may be taken, eg, assigning highest severity to the case, to ensure appropriate interpretation of the data. Further details, including additional estimands for the research questions on the effect of combined CVL-871 treatment group versus placebo and on the effect of final dose levels of CVL-871 following the completion of titration versus placebo, will be described in the SAP.

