4.4.3. Visit Windows

Analysis data will be summarized according to the scheduled visit time period for which they were recorded in the eCRF unless otherwise specified.

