11. PHARMACODYNAMICS

The planned timepoints for pharmacodynamic assessments are shown in the Schedule of Assessments (Table 4) which will be completed before the safety assessments and by the same identified caregiver.

All pharmacodynamic endpoints will be analyzed through descriptive statistical methods based on the mITT population. Pharmacodynamic endpoints with repeated post-baseline assessments will also be analyzed, using the mITT population, through statistical inference by using a mixed-model repeated measures (MMRM) analysis, including baseline score (if applicable), treatment, concomitant SSRI/SNRI use, visit (only measured at Visit 5 and 6), and the interaction between treatment group and visit as fixed factors in the model. Subject will be included as a random effect in the model.

An unstructured correlation matrix will be used to model the within-patient errors covariances. The Kenward-Roger approximation will be used to estimate the denominator of degrees of freedom. The least square (LS) mean of each treatment group, difference in the LS mean between the treatment groups, and the corresponding 80% and 95% CI of the differences and p-values will be provided.

If the MMRM model fails to achieve convergence due to complexity of model specification, different covariance structures will be used according to the following order till convergence is achieved:

1. Unstructured correlation (UN)
2. Heterogeneous Toeplitz (TOEPH)
3. Homogeneous Toeplitz (TOEP)
4. First-Order Autoregressive [AR(1)]
5. Compound Symmetry (CS)

The key research questions for the pharmacodynamic endpoints (ie, effect of CVL-871 treatment groups versus placebo) will be primarily addressed with a hypothetical strategy. As such, the missing values will be considered as missing at random (an MMRM analysis assumption).

The primary analysis for all PD endpoints will be performed as described above. However, if the number of subjects with evaluable baseline and post-baseline assessments for a specific PD endpoint is smaller than 15 (all treatment groups combined) or smaller than 2 in any treatment group, only descriptive statistical analyses will be conducted.

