15. CHANGES IN THE PLANNED ANALYSIS

In addition to changes corresponding to protocol amendments, the analysis plan differs from the protocol analysis section as shown below

- Protocol specified 80% CIs will be presented. The SAP further specifies that both 80% and 95% CIs will be included ([Section 11](#)).
- The population of all subjects who consent to participate in the clinical trial was referred as “Enrolled” in the protocol but is labeled as “Screened” for further clarity in the SAP ([Section 4.3](#)).
- The mITT population is modified in the SAP ([Section 4.3](#)) as compared with the protocol to allow analysis evaluates dose effect in this exploratory study.
- Due to the early closure of enrollment with the planned sample size not achieved, the hypothetical strategy is the only approach taken for missing value handling. The protocol specified sensitivity analyses are no longer planned.

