17.3. Missing Pharmacodynamics Data

Since the MMRM used for inferential analyses of pharmacodynamics data is a type of statistical model that handles missing data, no imputation is foreseen.

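### The SAP applies its hypothetical strategy only to values already missing, so scores observed after a prohibited medication starts enter the MMRM by default

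*SAP*

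**What the plan says.** Protocol 9.4.2 (repeated in the synopsis) defines the main pharmacodynamic (PD) estimand with "a hypothetical strategy to address intercurrent events (ICEs) of potential death, treatment discontinuations, missed visits, and start of prohibited concomitant medications". It allows a composite strategy where an event has a treatment-related reason, and leaves further details to the SAP.

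SAP 11 states that the key PD questions "will be primarily addressed with a hypothetical strategy. As such, the missing values will be considered as missing at random". SAP 15 says that, because enrollment closed early, "the hypothetical strategy is the only approach taken for missing value handling". SAP 17.3 adds that the MMRM "is a type of statistical model that handles missing data, no imputation is foreseen".

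The rule on which records are used is general. SAP 4.4.2 classifies assessments by their eCRF visit label, and SAP 4.4.3 says: "Analysis data will be summarized according to the scheduled visit time period for which they were recorded in the eCRF unless otherwise specified". Nothing is specified otherwise for scores recorded after an intercurrent event. SAP 17.6 reproduces the list of prohibited concomitant medications, but no PD analysis refers to it.

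**The concern.** A hypothetical strategy asks what the score would have been had the event not occurred. An MMRM under missing at random can target that, but only if scores affected by the event are first removed, so that the model treats them as missing. Saying that missing values are missing at random does nothing to a score that was observed after the event.

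If such scores stay in, those subjects are in effect handled by treatment policy, while subjects with missing scores are handled hypothetically. The reported contrast then mixes two estimands under one label.

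The protocol itself gives reasons to expect some prohibited medications to affect apathy. Psychostimulants are on the list, and Protocol 2.2.2 and 2.2.3 report that methylphenidate improved apathy. A newly started SSRI falls outside the stable-dose exception, and Protocol 2.2.1 says that SSRIs may worsen apathy. The shift could therefore go either way, and its effect on the contrast depends on the arm in which the event occurs.

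**Working it through.** **1. The plan's own figures.** The inputs are in Protocol 9.2: 75 randomized 1:1:1, 20% discontinuation, two-sided alpha 0.2, 80% power.
- Evaluable per arm: 25 x 0.8 = 20. Normal approximation to the detectable effect size: (1.2816 + 0.8416) x sqrt(2/20) = 0.671. The noncentral t with 38 df gives 0.678, as stated.
- For 60 randomized: 20 x 0.8 = 16 per arm, and the noncentral t gives 0.761, as stated.

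The sample size statement is not in error. The problem lies in the match between estimand and estimator.

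**2. Can scores after the start of a prohibited medication exist?** Yes.
- Protocol 9.4.2 lists this event separately from treatment discontinuation.
- Protocol 7.1 gives the need for a disallowed therapy as something that may lead to stopping IMP. It does not make stopping automatic.
- A subject who stays has the apathy scales at Weeks 6 and 12 (Schedule of Assessments).

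**3. Can scores after IMP stops exist?** Only narrowly.
- Protocol 7.1 encourages such subjects to stay for safety follow-up, and Protocol 7.2.3 ends IMP and trial participation together.
- The schedule has no PD scale at Visit 7 or at the final contact.
- What remains is the early-termination (ET) battery. It is the Visit 6 set, in a shared Visit 6/ET column. The SAP has no rule for the visit that it represents, so the eCRF label could place it at Week 12 whatever the study day.
- Subjects who do not tolerate Step 4 are already outside the SAP's mITT set.

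**4. Illustrative size.** The documents give neither event rates nor the final number randomized, so arm size n and number affected k are assumptions. Each affected subject is assumed to shift by the full reference effect of 1.8 points, with SD 3.2 (Protocol 9.2). Shift in the arm mean = 1.8 x k/n.

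| n per arm | k = 1 | k = 2 |
|---|---|---|
| 5 | 0.36 points (0.11 SD) | 0.72 points (0.225 SD) |
| 10 | 0.18 points (0.056 SD) | 0.36 points (0.11 SD) |
| 20 | 0.09 points (0.028 SD) | 0.18 points (0.056 SD) |

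Five per arm corresponds to the 15 subjects in total at which SAP 11 still permits the MMRM (15/3 = 5).

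**5. Against the noise.** With 10 per arm, the half-width of an 80% CI from a simple two-sample t is 1.33 x 3.2 x sqrt(2/10) = 1.9 points. Shifts of 0.18 and 0.36 points are about 9% and 19% of that.

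**6. Dilution at the planned size.** Assume 20 evaluable per arm, a true hypothetical effect of 0.678, and a share q of active-arm Week 12 scores recorded after an event, with none or half of the effect kept. Retained effect = 0.678 x (1 - q x (1 - share kept)).
- q = 5%: 0.644 to 0.661, power 77% to 78%.
- q = 10%: 0.610 to 0.644, power 74% to 77%.
- q = 20%: 0.542 to 0.610, power 66% to 74%.

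Setting the scores to missing (same q in both arms, missing at random true, no borrowing from Week 6) leaves the target at 0.678, with power 78%, 77% and 73%. The gain is mainly in estimating the declared quantity. When half of the effect is kept, power is about the same either way.

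**The case against.** The strongest reply is that the SAP never says that it keeps these scores. It is based on Protocol Version 4.0, and SAP 15 does not list any change to the events covered. On that view the estimand stands and only its implementation is underspecified. This is right about intent: a reader might infer that the sponsor knowingly replaced the estimand, and the documents do not show that. It does not remove the problem. The default rule keeps observed scores and no text overrides it, so a programmer following the SAP would include them. SAP 15 discloses that the composite option and the sensitivity analyses are dropped; it is silent on observed post-event scores.

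Second, such cases may be rare. Subjects likely to need prohibited therapy are excluded (exclusion criterion 16), and some who start one would stop IMP and have no later scheduled PD visit. This stands, and it limits the likely size.

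Third, the prohibited list is broad. It includes anticoagulants and opioids, for which the documents state no effect on apathy, so removal could discard informative scores. That stands as a cost. But the protocol's event is the start of any prohibited medication, and a narrower event would have to be declared.

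Fourth, safety is the primary objective, formal testing is not a key aim, and apathy-scale data and medications are listed. Affected records could therefore be traced afterwards. This limits the consequence, but the MMRM estimates, intervals and p-values would still carry the wrong label.

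**Conclusion.** The point holds for scores observed after a subject starts a prohibited medication and remains in the trial. Followed as written, the SAP includes them in the MMRM and does not estimate the hypothetical estimand that it declares. For stopping of IMP, the point holds only for the ET battery and its possible labelling as Week 12.

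Three stronger readings are not supported:
- Scores after IMP discontinuation do not generally stay in, because no PD visit is planned after Visit 6/ET.
- A material bias has not been shown. The shifts of 0.18 and 0.36 points rest on an assumed 10 per arm, one or two affected subjects, and a full methylphenidate-sized effect. Direction and frequency are unknown.
- Not every drug on the list can be said to affect apathy. For antipsychotics and bupropion, for example, the documents give no such evidence.

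The change should be made because it is cheap and because SAP 11 is the trial's only inferential analysis of the effect on apathy. It does not affect the primary safety analysis.

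**What to change.** In SAP 11:
- State that PD scores recorded after the start of a medication prohibited by SAP 17.6, including a breach of a stable-dose exception, are set to missing before the MMRM. Derive the flag from the medication dates and doses already collected (Protocol 6.5.1), and say whether the partial-date rule in SAP 17.2.2 applies.
- State that ET scores are assigned to Week 6 or Week 12 by actual study day within stated windows, and not automatically to Week 12. An ET score outside both windows is listed but not modelled.
- List the removed scores by arm, and report the MMRM on all observed data as a sensitivity analysis. SAP 15 would need a matching line, since it now says that the protocol-specified sensitivity analyses are no longer planned.

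The cost is a few sentences, a data flag, a listing and one further model run. A few observations leave the main model. That could bring an endpoint nearer to the 15-subject threshold below which SAP 11 allows only descriptive analysis.

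If the sponsor prefers to keep all scores, SAP 11 and SAP 15 should instead declare a treatment-policy strategy for the start of prohibited medication. The ET mapping rule is needed in either case.

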11.1. Neuropsychiatric Inventory-Clinician (NPI-C) and Neuropsychiatric Inventory Rating Scales

The NPI assesses 12 behavioral and psychiatric symptoms in dementia including domains for delusions, hallucinations, agitation/aggression, apathy, depression, euphoria, aberrant motor behavior, irritability, disinhibition, anxiety, sleeping, and eating (Cummings et al, 1994).

The NPI domain score for each domain is the product of frequency score \times severity score reported by the caregiver in response to clinician administered questions specific to each domain. Higher scores are indicative of more frequent and/or severe symptoms.

The NPI-C is a revised version of the original NPI and includes expanded domains and domain subitems, and a clinician rated severity score as the principle scoring methodology (de Medeiros et al, 2010). Unlike the NPI, the NPI-C allows the rater to obtain additional caregiver and patient information to inform the rating for each item within a domain.

The frequency and the severity of each behavior item are determined on 5-point (0 to 4) and 4-point (0 to 3) scales, respectively, based on caregiver interview responses. An additional rating of caregiver distress is included (6-point scale from 0 to 5). The clinician also observes and interviews the patient, when possible, to inform on the frequency of symptoms and overall clinical presentation. The clinician provides a clinical impression severity score for each item within the domain using a 4-point (0 to 3) scale, which is based on all available clinical (eg, medical records, personal observations, personal experience and training) and interview information.

An NPI-C total domain score based on the clinician impression can be calculated by summing the individual rating score for each domain item. Higher scores are indicative of more frequent and/or severe symptoms.

The instrument can be used as a stand-alone measure for specific neuropsychiatric domains (eg, dysphoria, apathy) or a combination of both (combination of domains with focus on one or more specific domains). Only the NPI-C apathy and dysphoria domains will be utilized as assessment measures in this trial and changes from Baseline to Weeks 6 and 12 will be analyzed through an MMRM for the mITT as described in Section 11. Other NPI-C domains will not be utilized. The NPI will be utilized to assess all 12 neuropsychiatric domains, including apathy and dysphoria, for confirmation of inclusion/exclusion criteria and for ongoing evaluation during the treatment phase.

Each NPI domain will be analyzed separately using an MMRM when sample size allows. In addition, all NPI and NPI-C data will be listed for the randomized patients with indicator for inclusion in the mITT analysis set.

11.2. Dementia Apathy Interview and Rating (DAIR)

The DAIR is a 16-item structured interview with the primary caregiver designed to assess illness-related changes in motivation, emotional responsiveness, and engagement (Strauss and Sperry, 2002). Each interview question consists of 2 parts: 1) how often a specific behavior was observed over the past month, and 2) whether the behavior in first item had changed from the time prior to memory loss.

Apathy item scores range from 0 (patient shows apathetic behavior almost never or less than once a week) to 3 (patient shows apathetic behavior almost always or almost every day). In their original form, higher levels of apathy could correspond to higher or lower scores, depending on the questions. Therefore, questions will be rescaled as follows, so that higher rescaled scores correspond to higher levels of apathy. For questions 1, 9, 11, 12, 13, and 14, rescaled score = original score, and for questions 2 - 8, 10, 15, and 16, rescaled score = 3 - original score. Items are counted for the total score only if the behavior represents a change toward apathy from pre-illness behavior. The total apathy score is a sum of all items reflecting change, divided by the number of items completed, with higher scores representing greater average apathy.

Changes from Baseline to Visit 5 (Week 6) and Visit 6 (Week 12) in DAIR score will be analyzed through an MMRM for the mITT as described in [Section 11](#). Individual DAIR items in their original form will be summarized through frequencies and percentages, regardless of whether or not they represented a change in apathy from pre-illness. Additionally, all DAIR individual related data will be listed for the randomized patients with indicator for inclusion in the mITT analysis set.

11.3. Apathy Evaluation Scale-Clinician (AES-C)

The AES-C is an 18-item rating scale which is completed by a clinician that measures apathy severity as defined by deficits in behavioral, cognitive, and emotional constructs of goal-directed behavior. Higher scores reflect greater apathy severity ([Marin et al, 1991](#)).

AES-C items are rated based on current subject's perception during the past 4 weeks. Ratings are based on the clinician's assessment of the patient's self-reports of AES-C items (perception during past 4 weeks) and rank from 1=Not at all characteristics to 4=A lot characteristic. In their original form, higher levels of apathy could correspond to higher or lower scores, depending on the questions. Therefore, questions will be rescaled as follows, so that higher rescaled scores correspond to higher levels of apathy. For questions 1-5, 7-9, and 12-18, rescaled score = 5 - original score, and for questions 6, 10, and 11, rescaled score = original score. AES-C total score is the total of items 1 through 18 after completion of the rescaling process and ranges from 18 to 72, with higher total scores corresponding to higher levels of apathy.

Changes from Baseline to Visit 5 (Week 6) and Visit 6 (Week 12) in AES-C score will be analyzed through an MMRM for the mITT as described in [Section 11](#). Additionally, all AES-C related individual data will be listed for the randomized patients with indicator for inclusion in the mITT analysis set.

11.4. Alzheimer's Disease Assessment Scale – Cognition Subscale (ADAS-Cog)

The ADAS-Cog is the most widely used general cognitive measure in clinical trials of AD. The original ADAS-Cog ([Rosen et al, 1984](#)) includes 11 items assessing cognitive function. The domains include memory, language, praxis, and orientation.

The modified ADAS-Cog13 ([Mohs et al, 1997](#)), which will be used in this trial, includes all original ADAS-Cog items with the addition of a number cancellation task and a delayed free recall task, for a total of 85 points. As in the parent instrument, higher scores indicated greater severity. The questionnaire and the scores will be provided by WCG VeraSci.

Changes from Baseline to Week 12 in ADAS-Cog13 overall score will be summarized through descriptive statistics for the mITT set. Additionally, all individual related data will be listed.

11.5. Modified Alzheimer’s Disease Cooperative Study–Clinical Global Impression of Change (mADCS-CGIC)

The original ADCS-CGIC focuses on clinicians’ observations of change in the subject’s cognitive, functional, and behavioral performance ([Schneider et al, 2009](#)). The original ADCS-CGIC has been modified specially for apathy in dementia.

Scoring is based on an interview with the caregiver by an independent, skilled, and experienced clinician with questions related to the severity of the subject’s overall clinical condition and apathy symptoms specifically.

Scores are on a 7-point scale where 1 is “marked improvement” and 7 is “marked worsening” with a rating of 4 representing “no change”. It is important to note that the assessment will reflect the subject’s current condition compared with their condition at baseline (Visit 2).

A baseline worksheet will be completed by the rater to assist in making all post-baseline comparisons and ratings.

The questionnaire and the scores will be provided by WCG VeraSci.

Descriptive statistics of the mADCS-CGIC scores will be presented by visit. Additionally, all mADCS-CGIC related individual data will be listed.

11.6. Modified Clinical Global Impression-Severity Scale (mCGI-S)

The mCGI-S is an observer-rated scale that will be used to measure both the severity of the subject’s overall clinical condition and their apathy symptoms specifically.

To perform this assessment, the investigator (or designee) will answer questions related to the severity of the subject’s overall dementing illness (cognition, behavior, and function) and apathy symptoms specifically, providing a severity rating score based upon their total clinical experience with the patient population and upon observed and reported symptoms, behavior, and function in the past 4 weeks. Scores are on a 7-point scale where 1 is “normal, not at all ill/no symptoms” and 7 is “among the most extremely ill patients/very severe symptoms”.

The questionnaire and the scores will be provided by WCG VeraSci.

Descriptive statistics of the mCGI-S scores will be presented by visit and change from Baseline to Visit 5 (Week 6) and Visit 6 (Week 12) in mCGI-S scores will be analyzed through an MMRM for the mITT as described in [Section 11](#). Additionally, all mCGI-S related individual data will be listed for the randomized patients with indicator for inclusion in the mITT analysis set.

